2.2.3.4 Dose Durations

The dosing duration for the 50 mg/kg, 75 mg/kg, 100 mg/kg, and 150 mg/kg inhaled doses have been established at 30, 45, 60, and 90 minutes.

Table 2.2-2 provides a summary of the dosing durations for each dosing group. Calculations used to derive these aerosolization times are outlined in this section.

Table 2.2-2. Dosing Duration in Minutes for Each Dosing Group

Weight (g)	Dose and Dosing Time (min)			
	50 mg/kg	75 mg/kg	100 mg/kg	150 mg/kg
750 – 2750	30	45	60	90

Note: Based on Bhutani, et al. ⁽¹⁵⁾

Neonates of low weight will receive slightly more study drug, while those with a higher weight will receive slightly less.

2.3 Study Duration

It is expected that recruitment will occur over a period of 7 months, with an average of 1 subject enrolled per 4 weeks for each of the approximately 12 study sites (actual subject recruitment period may vary). It is estimated that the last subject enrolled will complete all assessments and procedures within 9 months from the time of the first subject enrolled. Thus the total duration of the study is expected to be approximately 9 months.

Any adverse findings by the SRC may result in early study closure and early withdrawal of study subjects (Section 6).

2.3.1 Duration of Subject Study Participation

The total duration of study participation for each subject will be from enrollment (≤ 20 hours from birth) to 36 weeks PMA. All subjects who complete all assessments and procedures up to and including the Final Visit (to occur at 36 weeks PMA or NICU discharge or hospital transfer, whichever occurs first) will be considered study completers. Details regarding subjects who withdraw from the study before completion are provided in Section 10.

Study participation will consist of the following study periods (assessments, procedures, and visits associated with each of these phases can be found in Section 7.1):

- **Screening Period:** to occur in a timely manner to allow for study randomization ≤ 20 hours from birth.
 - Study consent must be completed before any study-specific screening procedures that would not otherwise be performed in accordance with standard of care and local institutional practices.
- **Primary Observation Period:** time of randomization (T_0 on study) to 48 hours from randomization.
 - To include: pre-treatment assessment, treatment period (30, 45, 60, or 90 minutes), followed by continual safety monitoring in accordance with local NICU procedures.
 - Study treatment must be initiated ≤ 22 hours from the time of birth
- **Extended Observation Period:** > 48 hours on study to completion on Study Day 7 (6 days after the day of randomization by calendar date) or until time of death or hospital transfer/discharge, whichever comes first.
- **Final Observation Period:** \geq Study Day 8 to 36 weeks PMA or discharge or until of death or hospital transfer/discharge, whichever comes first.

3 STUDY OBJECTIVES AND ENDPOINTS

This study is designed to investigate the safety and tolerability of lucinactant for inhalation in preterm infants of gestational age 26 to 28 completed weeks PMA. Safety and tolerability will be based on clinical evaluations (Section 8). Efficacy will be an exploratory objective. The endpoints specified are the same endpoints as Protocol 03-CL-1201, to allow for potential comparison and pooling of results.

3.1 Primary Objective

The primary objective of this study is to evaluate the safety and tolerability of lucinactant for inhalation, administered as an aerosolized dose in 4 escalating doses to a preterm, neonatal population 26 to 28 completed weeks PMA receiving nCPAP for RDS compared with neonates receiving nCPAP alone.

Safety and tolerability will be evaluated using the same measures and assessments that have been used in Protocol 03-CL-1201, which has shown lucinactant for inhalation up to 75 mg/kg to be generally safe and well-tolerated in infants 29 to 34 completed weeks PMA.

3.1.1 Primary Endpoints

The primary endpoints of this study will be derived from the safety evaluations, including adverse device effects (ADEs) reported from the time of randomization until 36 weeks PMA of upon discharge (Section 3.3).

3.2 Secondary Objective

The secondary objective of this study is to determine the maximum tolerated dose of lucinactant as determined by the safety evaluations obtained within each dosing group (Section 3.3), and to assess the feasibility of evaluating physiological pulmonary function parameters as a measure of improvement in clinical status (Section 3.4) in preterm infants 26 to 28 completed weeks PMA who are receiving nCPAP for RDS, compared with preterm infants receiving nCPAP alone.

3.3 Safety Evaluations

The following measures are to be documented in the electronic case report form (eCRF) in accordance with timings outlined in Appendix 2 and Section 7:

1. Survival (date and time of death if applicable)

2. AEs, including ADEs
 - To include: nasal excoriations by examination (≥ 24 hours to ≤ 7 days following aerosol exposure) and evidence of lung air leak (especially pneumothorax) (Section 7.1.8)
 - To be categorized as a peri-dosing events if onset of event is ≤ 2 hours from the time of initiating administration of lucinactant for inhalation [Section 9])
3. Signs consistent with worsening respiratory status (Section 7.5)
4. Concomitant medications (Section 7.3)
5. Use of respiratory support and supplemental oxygen (Section 7.6), to include:
 - Need for endotracheal intubation and mechanical ventilation
 - Need for intermittent positive pressure breaths using inflating pressures above the set CPAP pressure administered manually or mechanically through any patient interface
 - nCPAP and fraction of inspired oxygen (FiO₂) requirements (Section 5.4.1), (Section 7.6.2)
6. Complications of prematurity (ie, IVH, periventricular leukomalacia [PVL], pulmonary hemorrhage, NEC, patent ductus arteriosus [PDA], sepsis, ROP, BPD)
7. Physical examinations (Section 7.1.6)
8. Tolerability of lucinactant for inhalation
9. Incidence leading to withdrawal from study
10. Incidence of air leak
11. Assessments of the following:
 - a) PCO₂ (Section 7.1.5)
 - b) Serum electrolyte measurements (Section 7.1.7)
 - c) Body weight (Section 7.1.2)
 - d) Vital signs (Section 7.1.1)
 - e) Gastric liquid volume (Section 7.1.9)
 - f) Defecation (Section 7.1.10)
 - g) Oxygen (O₂) saturation, as determined by pulse oximetry (SpO₂) (Section 7.1.3)
 - h) Chest radiography, as applicable (Section 7.1.8)

3.4 Exploratory Efficacy Objective

To demonstrate the ability to measure clinical effect.

3.4.1 Efficacy Endpoints

Exploratory efficacy endpoints will be evaluated from the time of lucinactant for inhalation initiation until study completion (non-hypothesis testing) and will include the following:

1. Incidence of BPD
2. Rate of survival without BPD at 36 weeks PMA or upon discharge
3. Worsening of respiratory status (Section 7.5)
4. Technical performance of the ADS
 - The efficacy of the device delivery of lucinactant for inhalation will be characterized indirectly through the subject's response to treatment and solicited feedback from the PIs and relevant site-based study staff.
5. Physiological parameters (eg, FiO₂, PCO₂)

4 STUDY POPULATION SELECTION

4.1 Study Population

The study population will consist of approximately 64 preterm neonates from 26 to 28 completed weeks PMA with RDS who are candidates for SRT and nCPAP in a NICU setting. A subject will be enrolled at 1 of approximately 25 study sites in the US.

4.2 Inclusion Criteria

Each subject must meet all of the following inclusion criteria to be enrolled in this study:

1. Signed ICF from legally authorized representative;
2. Gestational age 26 to 28 completed weeks PMA;
3. Successful implementation of controlled nCPAP within 90 minutes after birth;
4. Spontaneous breathing;
5. Chest radiograph consistent with RDS; and
6. Within the first 20 hours after birth, requires an nCPAP of 5 to 6 cm H₂O to maintain SpO₂ of 88% to 95% with an FiO₂ of 0.25 to 0.50 that is clinically indicated for at least 30 minutes. Transient (<10 minutes) FiO₂ excursions below 0.25 or above 0.50 do not reset the 30 minute requirement.

4.3 Exclusion Criteria

Subjects meeting any of the following exclusion criteria may not be enrolled in this study:

1. A heart rate that cannot be stabilized above 100 beats/minutes within 5 minutes of birth;
2. Recurrent episodes of apnea occurring after the initial newborn resuscitation period (ie, 10 minutes after birth) requiring intermittent positive pressure breaths using inflating pressures above the set CPAP pressure administered manually or mechanically through any patient interface;
3. A 5-minute Apgar score < 5;
4. Major congenital malformation(s) and cranial/facial abnormalities that preclude nCPAP, diagnosed antenatally or immediately after birth;
5. Other diseases or conditions potentially interfering with cardiopulmonary function (eg, hydrops fetalis or congenital infection such as TORCH);
6. Known or suspected chromosomal abnormality or syndrome;

7. Premature rupture of membranes (PROM) > 2 weeks;
8. Evidence of hemodynamic instability requiring vasopressors or steroids for hemodynamic support and/or presumed clinical sepsis;
9. A need for endotracheal intubation and/or mechanical ventilation; and
10. Has been administered any the following:
 - a) Any investigational agent or exposure to a medical device,
 - b) Any other surfactant agent, or
 - c) Steroid treatment (steroid exposure before birth is acceptable).

Note: All subjects must continue to meet entry criteria at the time of initiation of study therapy.

5 STUDY DOSING AND ADMINISTRATION

Preterm neonates between 26 and 28 completed weeks PMA who are within the first 20 hours after birth and who had successful implementation of controlled nCPAP within 90 minutes of birth will be considered to be potential subjects. Qualification for study enrollment will be established after confirmation that the subject has met all of the inclusion criteria and none of the exclusion criteria. The clinical criteria for enrollment (eg, FiO₂, heart rate, O₂ saturation) may be met prior to informed consent being obtained; however, no study-specific procedures that are not part of the usual standard care of the subject at the institution may be performed until the informed consent has been provided by a legally authorized representative of the subject. As soon as study eligibility has been confirmed and the informed consent is signed, subjects will be randomized. All study subjects are to be randomized within 20 hours after birth to either an active study arm or a control arm. Subjects randomized to an active arm will receive 1 dose of lucinactant for inhalation, initiated within 2 hours of randomization through the investigational ADS device administered over 30, 45, 60, or 90 minutes in conjunction with nCPAP support. One additional treatment is allowed if subjects meet the repeat dose criterion. Subjects randomized to a control arm will be continued on nCPAP alone.

If at any point during the delivery of lucinactant for inhalation, a potential safety risk to the subject is identified, aerosolization must be discontinued by activating the ADS ‘Stop Treatment’ interface. Local NICU procedures should be followed in the event of early discontinuation of lucinactant for inhalation to ensure the safety and care of the subject. Any significant clinical findings or observations must be documented and communicated to Discovery at the earliest time point possible.

5.1 Precautions for Aerosol Delivery and Device Usage

The ADS, disposables, and study drug are investigational materials, and are to be used only for lucinactant for inhalation investigational studies, and are not to be used for any other purpose. All equipment and supplies are to be returned to Discovery at the end of the study.

Sites must maintain accurate records and proper storage of all delivered and dispensed study drug vials and device components (including the ADPs). Details on study supply accountability and storage are provided in Section 5.6 and in the ADS Operator’s Manual.

The PI or study-trained designee must provide close monitoring of the subject and study device during aerosol delivery.

5.1.1 Precautions for Aerosol Delivery

The device and interface used for nCPAP delivery during aerosol delivery must be commercially available for nCPAP delivery to neonates. During the nCPAP delivery, subjects must be closely monitored for complications related to placement of the patient interface. Assessment must include, but not be limited to, evaluations for the following conditions: bleeding, apparent obstruction of the nares, occlusion of interface requiring removal and replacement, nasal irritation (erythema of nares or septum, inflammation of nares or septum).

Local NICU policies and procedures for nCPAP delivery are to be used to deliver both the study drug and nCPAP, regardless of randomization (ie, active arm or control arm). After connecting the aerosol tube to the CPAP adapter and initiating aerosolization, the PI must ensure that the desired CPAP is maintained. During the dosing period, the subject's head should be securely but gently immobilized. Pacifiers can be used during dosing periods.

5.1.2 Stopping Criteria for Aerosol Delivery

The administration of lucinactant for inhalation may be discontinued at any time in accordance with the clinical judgment of the PI or the wishes of the subject's legal guardian. In accordance with local institutional practices, a proven SRT must be made available to subjects demonstrating a clinical need following exposure to lucinactant for inhalation. Reasons for discontinuation of lucinactant for inhalation may be related to but not limited to the following:

1. Device failure or malfunction, including error codes or treatment interruptions;
2. Pulmonary hemorrhage or other AE/ADE;
3. In the PI's best medical judgment, initiating or continuing the subject's exposure to lucinactant for inhalation is not in the best interest of the subject's safety, such as hemodynamic instability. (Note: When medical judgment is the sole criteria for stopping therapy, a detailed narrative describing the clinical events and observations supporting the decision to stop therapy needs to be documented.);
4. Signs of respiratory deterioration as evidenced by an increased respiratory rate or an observed increase in respiratory effort (work of breathing) plus at least one of the following:
 - An $\text{FiO}_2 \geq 0.70$ or a sustained (≥ 10 minutes) increase from baseline by ≥ 0.30 to maintain oxyhemoglobin saturation ($\text{SpO}_2 \geq 88\%$),

- A $PCO_2 > 70$ mm Hg or a progressive increase in PCO_2 from baseline to ≥ 20 mm Hg above baseline and confirmed with a blood gas,
- Recurring episodes of bradycardia defined as a heart rate of < 100 bpm for ≥ 20 seconds,
- A sustained apneic event, defined as apnea at least 20 seconds in duration and meeting at least one of the following: (1) HR < 100 bpm, (2) desaturation (oxygen saturation $< 80\%$), (3) requirement for IPP breaths using inflating pressures above the set CPAP pressure administered manually or mechanically through any patient interface.

5.1.3 Precautions for Device Usage

Before aerosol activation with the ADS, clinicians must have completed all required study training.

All local and regional NICU requirements for the operation of an investigational NICU device must be followed, to include any emergent or routine medical needs of the subject during and following aerosol delivery with the device.

If at any point during set-up, aerosol administration, or at finalization of aerosol delivery, an error screen or audible alarm is generated by the device that may signal a delivery malfunction, the user must immediately contact the clinical site monitor and call Discovery's reporting line ([name] [[contact]]). A representative from Discovery will call with further instructions. In such cases, the subject should be removed from the device, and all local institutional procedures must be followed to ensure continued safety and observation of the subject. The ADS Operator's Manual outlines audible alarms and visual displays that may be indicate delivery failure.

5.1.4 Assessment Parameters for Technical Performance of the Device

The following parameters will be captured in the eCRF:

1. Any issues associated with device tubing (eg, ventilator/CPAP tubing detachments, aerosol tube detachments, proximal pressure port obstruction, aerosol tube condensate obstruction).
2. Approximate volume (in ml) of liquid in all the traps.

3. Aerosol or study drug leakage before the subject interface (eg, disconnect of the inspiratory circuitry).
4. Occurrence of alarm signals before, during, or after dosing that may indicate a device malfunction.
5. Any automatic system shutdowns.
6. Loss of inspiratory flow to the neonate or inability to maintain nCPAP.
7. ADS temperature alerts (high or low).

5.2 Description of Study Assignment and Aerosol Delivery

The study treatment, ‘lucinactant for inhalation,’ consists of the investigational drug lucinactant and the delivery system ADS. The ADS has two components, the Aerosurf[®] Delivery Pack (ADP) and the Aerosurf[®] Control Unit (ACU). The rationale for the selected treatment and device technology is discussed in Section 2.2.

5.2.1 Aerosol Delivery

Preterm neonates between 26 and 28 completed weeks gestational age who are within the first 20 hours after birth and who had successful implementation of controlled nCPAP within 90 minutes of birth will be considered to be potential subjects. Qualification for study enrollment will be established after confirmation that the subject has met all of the inclusion criteria and none of the exclusion criteria. The clinical criteria for enrollment (eg, FiO₂, heart rate, O₂ saturation) may be met prior to informed consent being obtained; however, no study-specific procedures that are not part of the usual standard care of the subject may be performed until the informed consent has been provided by a legally authorized representative of the subject. As soon as study eligibility has been confirmed and the informed consent is signed, subjects will be randomized. All study subjects are to be randomized within 20 hours after birth to either an active study arm (consisting of lucinactant for inhalation in conjunction with nCPAP) or a control study arm (consisting of nCPAP alone).

Details for study drug preparation are provided in the Aerosurf Investigator’s Brochure and in the ADS Operator’s Manual. Briefly, 10 ml of sterile water for injection are added to each of 7 vials and the vials are gently inverted to mix the suspension. A total of approximately 60 ml of solution are drawn up into the provided ADP syringe, which is loaded into the ACU.

Study treatment is to begin within 2 hours after randomization. For subjects randomized to the active study arm, the treatment dose (ie, drug exposure) will be 50, 75, 100, or 150 mg

TPL/kg (delivered over 30, 45, 60, or 90 minutes, respectively) in accordance with the subject’s dosing group. A repeat dose at the same level is allowed if the repeat dosing criterion is met (see Section 5.2.5).

The carrier gas flow rate for the ADS is 3 L/min. This is consistent with the anticipated peak inspiratory flow (PIF) of preterm neonates (between 26 and 28 weeks PMA) and therefore will reduce potential aerosol dilution.

A summary of dose selection for this study is provided in Section 2.2.3.

5.2.2 Study Assignment; Dosing Groups

Subjects will be assigned to 1 of 4 dosing groups (Table 5.2-1).

Table 5.2-1 Study Assignments by Dosing Groups

Dosing Group	Study Assignment
Dosing Group I	Active Arm: (n = 8 subjects) Lucinactant for inhalation: 50 mg TPL/kg administered over 30 minutes with nCPAP 1 repeat dose is allowed if repeat dosing criteria are met Control Arm: (n = 8 subjects) Continuous nCPAP
Dosing Group II	Active Arm: (n = 8 subjects) Lucinactant for inhalation: 75 mg TPL/kg administered over 45 minutes with nCPAP 1 repeat dose is allowed if repeat dosing criteria are met Control Arm: (n = 8 subjects) Continuous nCPAP
Dosing Group III	Active Arm: (n = 8 subjects) Lucinactant for inhalation: 100 mg TPL/kg administered over 60 minutes with nCPAP 1 repeat dose is allowed if repeat dosing criteria are met Control Arm: (n = 8 subjects) Continuous nCPAP
Dosing Group IV	Active Arm: (n = 8 subjects) Lucinactant for inhalation: 150 mg TPL/kg administered over 90 minutes with nCPAP 1 repeat dose is allowed if repeat dosing criteria are met Control Arm: (n = 8 subjects) Continuous nCPAP

Note: Eligible subjects 26 to 28 weeks PMA will be randomized into either the active or control arm in accordance with the dosing group enrolling at the time of subject randomization:

5.2.3 Method of Assigning Study Subjects to Dosing Groups

For each dosing group, preterm neonates who successfully meet all eligibility criteria within the enrollment period (20 hours) will be randomly assigned to 1 of 2 study arms (active or control) (Section 5.2.2). Subjects will be randomized using centralized allocation by an interactive web response system (IWRS). Infants from multiple births will be randomized independently.

The randomization code list will be generated by Discovery Biometrics personnel and transmitted to the IWRS vendor. The code list will use a block size of 4 for each dosing group.

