Dose assignments will be un-blinded, as the primary objective of this study is safety and tolerability. Preliminary efficacy endpoints will be assessed as an exploratory objective.

All enrolled subjects will receive study treatment in a neonatal intensive care unit (NICU) , a specialized care center staffed by neonatologists, nurses, and respiratory therapists who are experienced in the delivery of emergent care to the preterm neonatal population. Infants in the NICU are continuously monitored using advanced and sophisticated monitoring equipment, and there is ready and immediate access to equipment, medications, and skilled personnel that may be needed to address emergent developments. Interventions such as endotracheal intubation, mechanical ventilation, and surfactant administration will be readily available to all study subjects if clinically indicated in accordance with the high level standard of care customary in the NICU.

Neonates will be followed through the primary phase evaluations through 36 weeks PMA, NICU discharge, hospital transfer, or death, whichever occurs first.

Study Population:

This study will be comprised of preterm neonates 26 to 28 completed weeks PMA who are receiving care in a NICU and are eligible to receive nCPAP support for RDS.

The study population will consist of 4 escalating dose groups with an allowed repeat dose if repeat dose criteria are met. Repeat dosing is to ensure subjects with a demonstrated need will receive additional treatment, as is done with bolus dosing.

- Study Sample Size:** It is anticipated that approximately 64 subjects will be enrolled. Approximately 32 subjects will be randomized to the active arm (drug/device combination) and approximately 32 subjects will be randomized to the control arm (nCPAP alone).
- The sample size is based on the number of subjects necessary to evaluate safety and tolerability of lucinactant for inhalation. Sample size calculations to demonstrate a clinical effect will not be performed as efficacy is an exploratory objective. Subjects that do not complete the administered dose of lucinactant for inhalation, or withdraw from the study will not be replaced, unless required by the SRC in order to adequately assess safety in the dose group.
- Number of Sites:** Up to approximately 25 clinical sites in the US; sites outside the US may also be used.

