13 STATISTICAL METHODS AND DETERMINATION OF SAMPLE SIZE

It is anticipated that approximately 64 subjects will be enrolled into the study with approximately 32 subjects randomized to the active surfactant arm. The sample size is based on the number of subjects necessary to evaluate the safety and tolerance of lucinactant for inhalation.

Sample size calculations to demonstrate clinical effect will not be performed as efficacy is an exploratory objective.

A complete outline of the all planned analyses for the study, to include the handling of missing data, is provided in Statistical Analysis Plan.

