13.3 Sample Size and Randomization

Sample size is not based on statistical estimation for this phase 2 study. The number of subjects randomized (approximately 8 in each active group and approximately 8 in each control group) will be considered sufficient to establish safety and tolerability before proceeding to the next higher dose. The total of approximately 32 subjects assigned to the active arm and approximately 32 subjects for the control arm for the entire study is considered sufficient to assess overall safety and tolerability.

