8 STATISTICAL TECHNICAL ISSUES

8.1 METHODS OF ASSIGNING SUBJECTS TO TREATMENT GROUPS

An overall randomization list will be prepared by Discovery's Biometrics department such that subjects will be randomly assigned to lucinactant or control (nCPAP alone). Each subject's random assignment will be provided to an interactive web response system (IWRS). As soon as possible after a subject meets the entry criteria and is eligible to be enrolled, the PI or authorized designee will log in to the IWRS and complete the randomization procedures. Subjects that discontinue the study prematurely will not be replaced.

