8.2 BLINDING/MASKING

This study is open label; thus, no blinding or masking procedures are employed.

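### The protocol prints a single fixed block size of 4 for an open-label trial; the risk of predicted assignments is limited but real, and nearly free to remove

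*Protocol*

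**What the plan says.** Protocol 5.2.3 allocates centrally through an interactive web response system (IWRS). On the list itself it says "The code list will use a block size of 4 for each dosing group" and "The randomization code list will be generated by Discovery Biometrics personnel and transmitted to the IWRS vendor". On siblings it says "Infants from multiple births will be randomized independently". Neither document says that the list is stratified by site, or who may see it.

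The trial is not masked. The protocol summary says "Dose assignments will be un-blinded, as the primary objective of this study is safety and tolerability", and SAP 8.2 says "This study is open label; thus, no blinding or masking procedures are employed".

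The intended sizes are "approximately 8 in each active group and approximately 8 in each control group" (Protocol 13.3), and Protocol 13 gives the total: "It is anticipated that approximately 64 subjects will be enrolled into the study with approximately 32 subjects randomized to the active surfactant arm".

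SAP 8.1 describes the list differently: "An overall randomization list will be prepared by" the sponsor's Biometrics department. It mentions neither blocks nor dosing groups. SAP 2.2.1 nevertheless gives 8 infants per arm in each of the four dosing groups.

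**The concern.** In an open-label trial, each assignment is known as soon as it is made. With one fixed block size that the reader also knows, past assignments reveal future ones: once two infants in a block have gone to one arm, the rest of that block is settled.

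This matters when the person who can predict can also influence who enters. Entry has numeric limits, but it also needs a radiograph judged consistent with RDS and an oxygen need judged clinically indicated (Protocol 4.2). SAP 8.1 has the investigator or a designee carry out the randomization, so the people who assess eligibility see the result at once.

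At stake is selection bias in small groups. One infant is 1/8 = 12.5 percentage points of an active dose group's event rate. Controls are pooled in the SAP, so one control infant is 1/32 = 3.1 points. Those are simply the weights of one infant. They show how little steering would be visible, not that any is expected.

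**Working it through.** **Inputs.** Block size 4, 1:1, per dosing group (Protocol 5.2.3). About 8 + 8 per group (Protocol 13.3). About 64 in total (Protocol 13). Number of sites: up to about 25 in the protocol summary, about 25 in Protocol 4.1, about 12 in Protocol 2.3. I use both ends.

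**The plan's own figure.** 16 / 4 = 4 blocks per group. Each block gives 2 active and 2 control, so 8:8 per group. Four groups give 32:32 = 64. The block size is consistent with the stated sample size.

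**Observer of the whole sequence who knows the block starts.** An assignment is certain when one arm is already used up within the block. Over the six possible blocks:

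| Position in block | Probability certain | Best guess correct |
|---|---|---|
| 1 | 0 | 1/2 |
| 2 | 0 | 2/3 |
| 3 | 1/3 | 2/3 |
| 4 | 1 | 1 |

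- Certain per block: 0 + 0 + 1/3 + 1 = 4/3. Share: (4/3)/4 = 33.3%, or 5.3 of 16.
- Best guess correct: (1/2 + 2/3 + 2/3 + 1)/4 = 70.8%, against 50% by chance.

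**Observer at one site.** Suppose the site contributes a share p of infants at random, and grant it knowledge of block positions, which is generous. It is certain only if it enrolled both infants that used up an arm:
- position 3: p² × 1/3; position 4: p²;
- share of its own infants: (p²/3 + p²)/4 = p²/3.

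| Assumed share p | Certain share p²/3 |
|---|---|
| 1/25 (25 equal sites) | 0.05% |
| 1/12 (12 equal sites) | 0.23% |
| 1/5 | 1.3% |
| 1/2 | 8.3% |
| 3/4 | 18.8% |

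With even enrolment, a site has 16/25 = 0.6 to 16/12 = 1.3 infants per dosing group, so the first two rows describe the plan as written.

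**Siblings randomized consecutively.** Within a block, the next infant goes to the opposite arm with probability 2/3; across a block boundary, 1/2. A group of 16 has 15 consecutive pairs, 12 within blocks and 3 across: (12 × 2/3 + 3 × 1/2)/15 = 63.3% in opposite arms, against 50% under independence. This assumes that no other site randomizes in between. The documents give no multiple-birth rate, so I cannot say how often it arises.

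**The proposed change.** Blocks of 4 and 6 can total 16 as 4 + 6 + 6 (active: 2 + 3 + 3 = 8), in random order.
- A block of 6 has 3/2 certain assignments. Even if the sizes and their order leaked, the total would be 4/3 + 3/2 + 3/2 = 4.3 of 16 (27.1%), below the present 33.3%. If they stay confidential, block ends cannot be read off.
- Consecutive opposite arms: (3 × 2/3 + 10 × 3/5 + 2 × 1/2)/15 = 60.0%. Varying the blocks barely helps with siblings, so they need a procedural rule.
- Largest temporary difference between arms: 3 infants, against 2 now.

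**The case against.** The strongest reply is that the one-in-three figure belongs to an observer whom the documents do not show. Allocation is central, sites enrol about one infant or fewer per dosing group, and a single site could be certain of almost nothing. A reader might infer that a third of assignments are predictable at the bedside; the documents do not support that. Nor do they give sponsor staff any role in confirming eligibility. Anyone who holds the list knows all of it whatever the block size, which is a question of access rather than of blocking. This part stands and limits the point.

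A reader might also infer that the protocol is wrong to call siblings independently randomized. The natural meaning is that each infant receives its own assignment, and read that way the sentence is correct. Choosing which sibling goes first gives no advantage to someone who has not followed the sequence, because each has a 50% chance before the first result is opened. What remains is the option of holding back or pressing forward the second sibling once the first result is known.

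A reader might see a contradiction between SAP 8.1 and Protocol 5.2.3. It is an omission: an overall list can cover four blocked groups, and the 8 per arm in SAP 2.2.1 rules out one unblocked list.

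Finally, nothing is tested, the SAP does not compare adverse events between groups, and small blocks keep the arms balanced if a hold occurs mid-group. The first two remove any effect on error rates but not selection bias, since the primary objective is still stated against nCPAP alone. The last is a fair argument for keeping blocks small. It is not an argument for publishing a fixed size.

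**Conclusion.** The point holds in limited form. The protocol discloses one fixed block size in an open-label trial with partly judgement-based entry. For an observer of the full sequence, 33.3% of assignments are certain on average and the best guess is right 70.8% of the time. For a single site the certain share is about 0.05% to 0.2%.

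The exposure is thus confined to three situations: people with a cross-site view, a site that enrols most of a dosing group (18.8% certain if it enrols three quarters), and siblings randomized back to back (63.3% in opposite arms).

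The site figures assume random spread over sites, a list not blocked by site, and known block positions. The sibling figure assumes consecutive randomization. No power or error rate is affected. There is no evidence that steering would occur; the case for change is that the protection costs almost nothing.

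**What to change.** 1. **Protocol 5.2.3:** delete the block size. Use randomly varying block sizes that still total 8:8 per dosing group, for example 4 and 6 in random order. Record them only in a restricted randomization specification, and limit access to the list to people outside the study team.
2. **Siblings:** change *randomized independently* to *randomized individually*. When siblings are eligible at the same time, record both eligibility decisions before opening the first assignment, then randomize in birth order. Do not delay an infant whose sibling is not yet eligible, because Protocol 5.2.1 randomizes as soon as eligibility is confirmed and consent is signed.
3. **SAP 8.1:** state that the list is blocked within dosing group, without giving the sizes.

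The cost is a new code list in the existing IWRS, a short restricted document and a few sentences of wording. The downside is a slightly larger temporary imbalance, at most 3 infants rather than 2. That matters little but is not nil, because the enrollment holds and unscheduled safety reviews in Protocol 6.2 and SAP 7.2 can act before a group is complete. One residue remains: someone who follows the whole sequence and knows that a group closes at 8:8 can still deduce the final assignment.
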